1. INTRODUCTION AND RATIONALE

Disorders of long-chain fatty acid beta-oxidation (FAO) comprise genetic deficiencies of fatty acid transport from the cytosol to the mitochondrial matrix and mitochondrial beta-oxidation of acyl-CoA compounds with a chain length of 14-20 carbon atoms. One of the most common long-chain fatty acid oxidation defects in humans is very long-chain acyl-CoA dehydrogenase deficiency VLCADD (OMIM 201475, EC 1.3.99.13; [1]). Impairment of energy production from exogenous or endogenous fatty acids is the most prominent feature of VLCADD [1]. Clinical symptoms, therefore, arise or are exacerbated during catabolic situations e.g. during exercise, illness or fasting when lipids are released from endogenous stores and have to be used as energy substrate. Organs most frequently involved are those using long-chain fatty acids as primary energy source, such as the heart and skeletal muscles. Age at onset, manifestation patterns and clinical severity differ between patients. The most severe presentations are Reye-like symptoms, cardiomyopathy and SIDS (sudden infant death syndrome) in the neonatal period. Milder clinical phenotypes manifest with hypoketotic hypoglycaemia during intercurrent illness and exercise-induced skeletal myopathy as well as episodic rhabdomyolysis. Patients may present with different symptoms at different ages.

Rhabdomyolysis

One of the most prominent symptoms of VLCADD patients is myopathy [1,2]. It most often involves the breakdown of muscle (rhabdomyolysis). Myopathy is provoked by fasting, fever, cold, medication and exercise from infancy to adulthood, but often has its onset in adolescence. In clinical practice, parents of pediatric patients and adult patients themselves wonder therefore to which extent they will be able to perform exercise. The pathophysiology of myopathy and rhabdomyolysis in general is not completely understood. The likely mechanisms behind the exercise-induced rhabdomyolysis and myopathy in VLCADD are a failing compensatory mechanism during requirement of extra energy (eg during exercise, fever, fasting). The symptoms are thought to result from one or more different pathophysiological mechanisms: (i) energy shortage in (exercising) muscle due to the FAO defect; (ii) toxicity caused by the accumulation of FAO intermediates. Reported muscle biopsies show a range from normal muscle fibre structure, to diffuse lipid accumulation and aspecific abnormalities. No ragged red fibres have been reported. Based on the recurrent episodes of rhabdomyolysis, myopathy in VLCADD might also be caused by meta-inflammation: inflammation caused by abnormal metabolites. The accumulation of long chain acylcarnitine esters has been implicated in muscle pathology in VLCADD, particularly in the heart. But, there is also evidence that ischemic changes in heart

[figure not shown]
might be due to impaired energy production rather than from long chain acylcarnitines accumulation, emphasizing the importance of available free carnitine to recycle CoA.

Therapy in VLCADD.

Clinical management of VLCADD patients poses a major challenge. At present, there is no effective therapy to alleviate the debilitating condition of severe exercise intolerance and myalgia with risk of episodic rhabdomyolysis [3]. Patients are typically advised to engage only in light physical work in combination with timely and ample intake of carbohydrates and/or medium-chain triglycerides (MCT). It has, however, long been hypothesized that nutritional ketosis (NK) could be highly beneficial to patients with metabolic myopathies such as VLCADD [4]. Amongst others, ketone bodies could take on the role of primary energy source in exercising muscle. The problem has been, however, that, until now, no vehicle for establishing NK in humans without undesired side effects has been available [4].

Ketone bodies the evolutionary adaptation to power metabolism

Ketone bodies, acetoacetate and D- β -hydroxybutyrate, are the metabolic response to energy crisis, representing a powerful evolutionary mechanism to sustain life by altering oxidative fuel selection [5]. The teleological advantages of ketone body metabolism are clear during conditions where survival of the organism depends upon optimal mitochondrial efficiency, and conservation of fuel reserves. Ketosis may also provide thermodynamic advantages over other carbon substrates by increasing the free energy conserved in ATP (ΔG_{ATP}) by the oxidation of ketones during mitochondrial oxidative phosphorylation [6]. The combination of improved energetic efficiency and fuel sparing is vitally important not only during famine, but could also provide clues to new methods of sustaining human performance. Recent work within the group of collaborator [name] at University of Oxford on the effects of oral administration of ketone bodies during exercise has demonstrated a significant, 4% improvement in the power output of elite athletes over 30 minutes (seated rowing ergometer; Figure below; [7]). This degree of improvement in this population of athletes is of significant competitive advantage.

The effects of acute nutritional ketosis on physical performance in athletes.

(A). Protocol and nutritional composition of ketone and control drinks. (B). blood concentrations of ketone body over time showing increased ketosis after ingestion of ketone drink and oxidation of ketone from blood stream during exercise. (C). Bland-Altman plot of performance. (D) Uniform performance improvement over all weight and gender classes of athlete. (E). Power profiles over 30 min of maximal exercise, with a 4% greater power output in the ketone arm at the end of exercise vs. control. (from [7]).

[figure not shown]
Harnessing ketosis for the preservation of muscle performance

In order to harness the physiological advantages of ketosis, a ketone ester was developed to deliver nutritional ketosis without elevations in fatty acids, or depletion of carbohydrate reserves (as is seen in starvation or endogenous ketosis) [8]. This exogenous form of ketosis enables the creation of a novel physiological condition with which to re-evaluate human performance, and metabolic regulation. Developed by TDeltaS Ltd. in association with the University of Oxford, this nutritional ketone body is not commercially available and to this point has been tested on over 200 people without adverse effects The safety, tolerability and toxicology profile of this ester has been published previously [9]. The drink has been designated as GRAS by the FDA allowing it to be used as a foodstuff in the USA. The ketone ester has previously been used in clinical research by [name] at the University of Oxford; LREC reference numbers O7/Q1605/37, 10/H0605/10, 11/SC/0223, 14/EE/0063, and 14/LO/0288 as well as in previous work conducted in partnership with the UK military MODREC 298/PPE/11. In accordance with University of Oxford policy, the Intellectual property rights to this ketone ester are linked to an investigator ([name]) who has a declared interest.

Ketosis alters muscle fuel metabolism in working muscle

Strong supportive evidence for the importance of ketosis in altering working muscle metabolism dates back in excess of 60 years. Most notably the work of Randle in 1963, who demonstrated that the presence of ketone bodies inhibits glycolytic flux and increases the quantity of glycogen in both rat cardiac muscle and diaphragm [10]. The thermodynamic potential of ketosis was shown by Kashiwaya and colleagues, who demonstrated a dramatic 28% increase in hydraulic efficiency over glucose by the addition of ketones to the perfusate of a working heart model [11].

We have recently characterised the effects of nutritional ketosis on skeletal muscle metabolism, showing the clear evolutionary advantages of ketosis in sparing not only carbohydrate and fat metabolism, but in preserving muscle protein breakdown. The metabolic alterations induced by nutritional ketosis on the major energy pathways before and after exercise in humans are shown below.

The effects of nutritional ketosis on muscle metabolism before (pre) and after (post) 1 hour of exercise at 75% of W_{Max} . **(A)** Branched chain amino acid (BCAA) concentrations are significantly reduced following ketosis vs. other nutritional substrates. **(B)** Branched chain amino acid levels in muscle are related to pyruvate levels as the end products of glucose breakdown. **(C)** Conservation of muscle BCAA is proportional to the muscle ketone concentration, as a result of ketone bodies reducing muscle glucose use **(D)**. **(E)** Schematic representation of the differences between fat and glucose metabolism in exercise are shown vs. ketosis **(F)**. (From: [7])

Nutritional intervention in metabolic myopathy

Enzymatic deficiencies affecting the metabolism of fats are multiple, albeit rare disorders characterized by consistent clinical phenotypes. The primary symptoms of defective metabolism of fat vary in severity depending on the metabolic location of the defect, and the degree of expression. However common to almost all conditions are an intolerance of exercise, skeletal or cardiac muscle myopathy, and a reliance on exogenous dietary fuels to sustain muscular energy demands.

Whilst the mainstay of therapy for these patients is the maintenance of blood borne substrates via adherence to various diets [12-14], these regimes are often inadequate to allow a normal physical lifestyle. In severe cases muscle damage, and other organ dysfunction reduces life expectancy and can render patients severely incapacitated. An alternative nutritional strategy to supply fuels in the form of ketone bodies may offer a new approach in the management of these conditions, without the unwanted effects of bolus glucose intake [3], or unpalatable dietary intervention.

Ketosis in metabolic myopathy

Previously, inducing a physiological ketosis required unpleasant Atkin's style high fat, low carbohydrate diets [15], or infusions of dissolved ketones salts [16]. Neither of these methods are applicable in VLCAD deficiency for obvious reasons. Now it is possible to deliver nutritional ketone bodies in drink form, making the oral nutritional delivery of ketones possible for the first time in humans [7]. This proposal seeks approval for a first clinical investigation into the possible benefits of acute NK delivered via the ketone ester drink in human VLCADD patients, specifically the metabolic basis for any enhanced muscle function.

Collaboration with the Dutch VLCADD expertise centre

Since 2007 Very Long Chain Acyl-CoA Dehydrogenase Deficiency (VLCADD) is included in the Dutch neonatal screening program (NSP). VLCADD is a rare disease (1:80000) and has only been discovered recently in 1992. Knowledge about disease course and long term effect of therapy is scarce. Therefore, the UMC Utrecht in collaboration with the Laboratory Genetic Metabolic Diseases (Academic Medical Center Amsterdam) and RIVM started an expertise centre in which all patients with VLCADD in the Netherlands can be seen. The primary goal of this expertise center is to document the clinical and biochemical phenotype and disease course of all diagnosed VLCADD patients in the Netherlands (METC nr 10-430/C). The Center partakes in the present investigative team to investigate the clinical benefits of acute NK in human VLCADD ([name]). The PI of the present application ([name]) has

previously collaborated with the center in a clinical investigation into muscle ATP metabolism in VLCADD patients (protocol **12-211/K** (UMC Utrecht)).

Inclusion of adolescent patients

Due to the rarity of the disease this study will include patients from the age of 16 years that could benefit from NK as well. Since rhabdomyolysis often has an onset in adolescence, confirmation of our hypothesis would lead to therapeutic use in that age group as well. Moreover, older patients often suffer from severe exercise intolerance and loss of muscle function due to earlier episodes of rhabdomyolysis, leaving most of them unable to complete our study protocol. Originally, all adult VLCADD patients known by the Dutch expertise center were provided with information on the study. Unfortunately, 1.5 years after the first inclusion only four patients participated. The main reason the other patients did not want to participate was the intensity of the protocol. Although the exercise test is at moderate intensity, the physical condition of these patients withholds them from riding a bike. Therefore an amendment was made to the original protocol to lower the minimum age to 16 years to reach sufficient power for this study. Unfortunately not many adolescent patients are known in The Netherlands, lowering the minimum age to 16 years will make participation possible for one patient. Lowering the minimum age even further won't make a difference, since the patients between 10-16 years are both rare and severely affected.

In vivo ³¹P MRS read-out of muscle mitochondrial performance

Phosphorus magnetic resonance spectroscopy (³¹P MRS) allows for non-invasive read-out of intramuscular pH and concentrations of Pi, PCr and ATP in human tissues (17). As such, dynamic ³¹P MRS recording of these metabolic variables in muscle offers a window onto the integrated *in vivo* performance of the cellular metabolic networks that produce ATP from the breakdown of fat and carbohydrates to maintain energy balance during exercise. ³¹P MRS-derived parameters such as the rate constant of PCr and Pi recovery post-exercise offer unsurpassed indices of *in vivo* mitochondrial function that have proven most useful in the clinical investigation of human metabolic myopathy (17). Recently, we applied this method to investigate energy balance in quadriceps muscle of VLCADD patients during an endurance exercise task (Diekman, manuscript in preparation). We found no evidence for impaired mitochondrial ATP synthetic function. However, changes in Pi and PCr during a standardized in-magnet bicycling exercise test were threefold larger than in healthy controls suggesting lower contractile efficiency of VLCADD muscle. Such a muscle phenotypic adaptation would aggravate the problem in VLCADD of exclusive dependence on turnover of the finite muscle carbohydrate store for ATP production, in turn explaining the known elevated risk for exertional rhabdomyolysis in VLCADD (Diekman, manuscript in preparation). Conversely, these results suggest that any boost of muscle mitochondrial function from acute NK should

be an effective therapy to improve exercise tolerance and lower the risk of exertional rhabdomyolysis in VLCADD.

2. OBJECTIVES

1. To investigate the potential of a novel dietary substrate preparation to enhance muscle mitochondrial function in VLCADD via acute nutritional ketosis.
2. To investigate if tri-citric acid cycle substrate supply in muscle of patients with VLCADD is boosted by acute nutritional ketosis.

3. STUDY DESIGN

This is a randomised, blinded, placebo controlled, two-way cross over trial. Patients with VLCADD will be recruited by the VLCADD Expertise Center at UMC Utrecht. Nutritional ketosis will be compared to a placebo, delivered as an isocaloric drink before exercise. An individualised, standardised bicycle exercise protocol will be completed by each participant with collection of blood metabolites, respired gases, and subjective ratings of fatigue and muscle complaints. In addition in vivo ³¹P MR Spectroscopic recordings will be made from the quadriceps muscle before (resting), during and post-exercise. An optional muscle biopsy will be obtained from the quadriceps before and after exercise.

Patients will be asked to participate in three study sessions:

session I (site: nearest Academic Medical Center, Pediatric test ward).

- standard maximal cardiopulmonary exercise test (CPET; bicycle ergometry with indirect calorimetry)
objective: determination of VO_{2max} in order to set the desired exercise workload of maximal individual rate of fat oxidation (FATMAX; typically ~40% MVO_2) in sessions II and III below.
- venipuncture
objective: measure rise in blood lactate and creatine kinase (CK) levels in response to CPET

sessions II and III (site: Neuroimaging Magnetic Resonance Center UMC Groningen).

- venipuncture + canulation
objective: prepare subject for serial (every 10 min) blood sampling for off-site metabolic profiling
- oral intake of nutritional drink A or B (ketone and placebo drinks, respectively)
Each subject will receive both drinks over the course of the trial in a blinded fashion – i.e., if drink A in session II, then drink B in session III, and vice versa.
- microbiopsy from the quadriceps muscle (optional)
*1st biopsy: 20 min after oral drink; 2nd biopsy: immediately following end of exercise bout.
objective: metabolomic profiling of the state of the energy metabolic network in muscle and mapping of individual phenotypic muscle properties (fiber type, mitochondrial density, capillary density). Biopsies will be obtained from the m. vastus lateralis of the left leg. Hereto, a preparatory superficial incision of the skin and fascii will be made under local sedation and bandaged, allowing fast and reproducible biopsy sampling prior to and immediately following exercise bout 1 below.*

- 40 min upright bicycling exercise at FATMAX outside MR scanner (exercise bout 1)

Blood samples are collected every 10 minutes.

Subjects state subjective fatigue and muscle ache following exercise bout.

- microbiopsy from the quadriceps muscle (optional)

Biopsies will be obtained from the m. vastus lateralis of the left leg (see above).

- 5 min supine bicycling exercise at FATMAX inside MR scanner (exercise bout 2)

*serial in vivo 31P MR spectra will be recorded non-invasively from the m. vastus lateralis of the right leg as previously (protocols **12-211/K** (VLCAD; UMC Utrecht); **NL41313.042.12** (MCAD; UMG) to determine energy and proton balance in the muscle during exercise and the kinetics of metabolic recovery following exercise. Subjective fatigue and muscle ache scores and a blood sample will be taken after the subject has exited the scanner room. Final blood samples including on-site analysis of CK levels are taken up to 3 hr post-session III to monitor any rhabdomyolytic event.*

- 24 hours after session II and III, co-investigator [name] will call each subject to evaluate subjective fatigue and muscle complaints after the subject left the test facility.

Time interval between study sessions I and II will be at least 7 days; between study sessions II and III: 7 days. The night prior to sessions II and III, patients will be housed in close vicinity to the UMCG. Patients will be instructed to take a late evening snack or meal according to their individual record of maximal fasting duration, given a start time of the study at 08:00 am the following day. Patients will be allowed a light breakfast according their normal diet before they will receive the caloric drive before the test. The breakfast will be the same for session II and III.

The total duration of the first session will be around 45 minutes, with 30 minutes of preparation and 8-12 minutes of cycling (exact time length dependent on the maximal endurance of the participant). The total duration of the second and third session will be around 5 hours including 45 minutes of preparation, 45-60 minutes of bicycling for the submaximal endurance exercise test and 3 hours of post-exercise resting where after the last blood and urine sample will be collected. During this 3 hour period, participants will be asked to fill out a HAES diary and can watch a DVD to pass time.

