 - HAES score questionnaire
- Muscle:
 - resting quadriceps phosphocreatine (PCr) and inorganic phosphate concentrations; pH
 - exercise quadriceps phosphocreatine (PCr) and inorganic phosphate concentrations; pH
 - post-exercise rates of recovery of quadriceps PCr, Pi and pH
 - optional: resting and post-exercise muscle levels of glycogen, lactate, 3-OH butyrate, and (very) long (C18-C14) to medium (C12-C8) to short chain (C6-C2) acetyl-carnitines (on a patient-voluntary basis)
- Blood:
 - levels of 3-OH butyrate, glucose, bloodgas, lactate, acylcarnitines and creatine kinase at rest and post-exercise
- Urine: myoglobine

Nature and extent of the burden and risks associated with participation, benefit and group relatedness: In clinical practice, many patients with VLCADD wonder to which extent they are able to exercise safely. Any means of boosting this capacity will greatly improve the quality of life and long-term health in this patient population. Acute nutritional ketosis after ingestion of a novel edible ketone ester is a very promising novel therapy towards this aim and has already been tested with positive effects in human athletes. This study will gain insight whether a sound metabolic basis exists for its therapeutic use in this patient population.

Patients will be asked to participate in three study sessions:

session I (site: nearest Academic Medical Center, Pediatric test ward).

- standard maximal cardiopulmonary exercise test (CPET; bicycle ergometry with indirect calorimetry)

objective: determination of VO_{2max} in order to set the desired exercise workload of maximal individual rate of fat oxidation (FATMAX; typically ~40% MVO_2) in sessions 2 and 3.

- venipuncture

objective: measure basal metabolic profile and rise in blood lactate and CK levels in response to CPET.

sessions II and III (site: Neuroimaging Magnetic Resonance Center UMC Groningen).

- venipuncture + cannulation

objective: prepare subject for serial (every 10 min) blood sampling for off-site metabolic profiling

- oral intake of nutritional drink A or B (ketone and placebo drinks, respectively)

Each subject will receive both drinks over the course of the trial in a blinded fashion – i.e., if drink A in session II, then drink B in session III, and vice versa.

- microbiopsy from the quadriceps muscle (optional)

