1st biopsy: 20 min after oral drink; 2nd biopsy: immediately following end of exercise bout 1. objective: metabolomic profiling of the state of the energy metabolic network in muscle and mapping of individual phenotypic muscle properties (fiber type, mitochondrial density, capillary density). Biopsies will be obtained from the m. vastus lateralis of the left leg. Hereto, a preparatory superficial incision of the skin and fascii will be made under local sedation and bandaged, allowing fast and reproducible biopsy sampling prior to and immediately following exercise bout 1 below.

- 40 min upright bicycling exercise at FATMAX outside MR scanner (exercise bout 1)

Blood samples are collected every 10 minutes.

- microbiopsy from the quadriceps muscle (optional)

Biopsy will be obtained from the m. vastus lateralis of the left leg (see above).

- 5 min supine bicycling exercise at 50% MVO_2 inside MR scanner (exercise bout 2)

*serial in vivo ^{31}P MR spectra will be recorded non-invasively from the m. vastus lateralis of the right leg as previously (protocols **12-211/K** (VLCAD; UMC Utrecht); **NL41313.042.12** (MCAD; UMG) to determine energy and proton balance in the muscle during exercise and the kinetics of metabolic recovery following exercise. A blood sample will be taken after the subject has exited the scanner room. Final blood samples including on-site analysis of CK levels are taken up to 3 hr post-session III to monitor any rhabdomyolytic event.*

- 24 hours after session II and III, co-investigator [name] will call each subject to evaluate subjective fatigue and muscle complaints after the subject left the test facility.

Time between study sessions I and II will be at least 7 days; time between study sessions II and III will be 7 days. For session I, patients will be asked to abstain from food 3 hrs prior to the test. For sessions II and III, participants will be asked to keep a 'food diary' for the week prior to the test in order to monitor the caloric intake and macronutrient content of each participant. For sessions II and III, patients will travel to Groningen the evening prior to the study and will be housed in a hotel across the street from UMCG. Patients are able to take a

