8.1.2 Secondary study parameters/endpoints

- completion of 40 min upright bicycling bout at FATMAX (yes/no; if no, #minutes)
- completion of 5 min supine bicycling bout at FATMAX in scanner (yes/no; if no, #minutes)
- subjective fatigue and muscle ache score after each exercise bout (scale 0-10) and 24 hours after exercise
- blood levels of 3-OH butyrate, acetoacetate, acylcarnitines, glucose, lactate and pH prior to and post-exercise.
- optional: muscle levels of glycogen, lactate, 3-OH butyrate, and (very) long (C18-C14) to medium (C12-C8) to short chain (C6-C2) acetyl-carnitines prior to and immediately post-exercise (on a patient-voluntary basis)

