Blood samples of 1-2 ml will be drawn via a 3-way tap from a 22 G venous canula (for subject comfort) inserted into a forearm vein at the start of each study visit. Blood samples

for free fatty acids, glucose and other assays will be taken and stored on ice, subsequently centrifuged, and stored at -80 until further processing. Up to 7 samples will be taken from the canula (~15 ml of blood total): #1 and #2 at baseline (in duplo), #3-5 during exercise (every 10 min), #6 after 40 minutes of moderate-intensity exercise, and #7 after the final MRS-analysis when the participant has recovered from exercise.

Muscle biopsy:

Participants are given the option at the start of the trial of undergoing muscle biopsy. If the patient has given informed consent to muscle biopsy, samples will be taken before and after exercise testing protocol during one or both study visits (2 samples/run; maximal of four biopsies for the complete study). 0.25 gm. of muscle tissue will be collected using percutaneous needle biopsies from the lower third of the Vastus Lateralis muscle with a biopsy gun (Bard Monopty, Bard Biopsy Systems, USA; a sterile standard biopsy technique (SOP). Muscle biopsy will be obtained from new incisions under local anaesthesia. Tissue samples will be frozen immediately in liquid nitrogen and stored at -80 °C until further analysis. Assays include glycogen and the metabolites of the glycolytic, TCA cycles. If sufficient tissue is available, enzymatic activity of mitochondrial and cytosol proteins, muscle fibre types, amino acids, and fat stores will also be determined.

Storage of tissue samples

All samples will be frozen immediately and stored at -80°C in the laboratory for Liver, Digestive and Metabolic diseases of the department of Paediatrics at UMCG.

31P MRS

MR data gathering will be performed using a 3.0 T whole-body MR-scanner (Intera; Philips Medical Systems, Best, The Netherlands). Subjects are introduced to the scanner and exercise apparatus and instructed. MRS data gathering will be performed with a surface coil wrapped over the quadriceps muscle. Conventional anatomical MRI scans will be acquired for positioning and scanner preparation. 31P MR spectra will be acquired serially to measure dynamics in intramuscular PCr, ATP, Pi, and pH using standard 31P-MRS protocols.

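### On-site CK for rhabdomyolysis is specified only after session III, so a reviewed CK result from session II is not assured before the last exercise session

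*Protocol*

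**What the plan says.** Each patient has a maximal exercise test (session I) and two endurance sessions (II and III), one with each drink. On rhabdomyolysis monitoring, Section 3 states: "Final blood samples including on-site analysis of CK levels are taken up to 3 hr post-session III to monitor any rhabdomyolytic event". The session description in the Summary uses the same wording.

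Other text bears on when CK is measured:

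- **Session I (Section 3):** the blood draw is there to "measure rise in blood lactate and creatine kinase (CK) levels in response to CPET".
- **Sessions II and III (Section 3):** both include "3 hours of post-exercise resting where after the last blood and urine sample will be collected". The assays to be run on that sample are not named.
- **Summary, blood parameters:** the list ends with "acylcarnitines and creatine kinase at rest and post-exercise" and names no session. Urine myoglobin is listed in the same way.
- **Section 8.1.2:** the blood endpoints are "blood levels of 3-OH butyrate, acetoacetate, acylcarnitines, glucose, lactate and pH prior to and post-exercise". CK is not among them.
- **Section 8.3:** up to seven cannula samples are described, the last being number "7 after the final MRS-analysis when the participant has recovered from exercise". Neither CK nor a 3-hour time point is mentioned.

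On spacing, Section 3 gives: "Time interval between study sessions I and II will be at least 7 days; between study sessions II and III: 7 days". After sessions II and III an investigator telephones each patient at 24 hours to ask about fatigue and muscle complaints.

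**The concern.** The protocol treats exertional rhabdomyolysis as the main hazard of exercise in this disease, and its Summary says that episodes can leave permanent muscle damage. A check for that hazard is most useful between the two endurance sessions, when its result can still change what happens next. Read literally, the protocol puts the on-site check after the second of them.

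The 24-hour call does come between the sessions, but it asks about symptoms. The burden footnote in the Summary expects the endurance test to cause temporary muscle pain in some patients, so complaints alone may not separate expected soreness from muscle breakdown. What is at stake is a patient with an unrecognised episode after session II returning a week later for the same exercise.

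**Working it through.** The protocol gives no figure to reproduce, so the check is to set the relevant texts side by side and ask one question: does any of them assure a CK result from session II, in hand and reviewed, before session III?

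1. **On-site CK sentence (Summary and Section 3).** It names session III only, in both places. The next item in each list, on the 24-hour call, names both II and III. The authors therefore wrote both numerals where they meant both, at least there. Answer: no.
2. **3-hour blood and urine sample (Section 3).** It is drawn in session II as well as III, so a suitable sample exists. Assay, place of analysis and turnaround are not stated. Answer: possible, not assured.
3. **CK and urine myoglobin in the Summary list.** There is no limit to a session, so CK may well be measured at session II. Nothing says when the result is read or who acts on it. Answer: possible, not assured.
4. **Sections 8.1.2 and 8.3.** CK is absent from the endpoint list and from the numbered samples. Section 8.3 has blood samples stored frozen for later processing, and Section 3 gives off-site profiling as the purpose of the serial samples. Answer: no.
5. **Session I CK.** This follows a maximal test of 8 to 12 minutes. It shows the response to that test, not to 40 minutes of endurance exercise followed by 5 minutes in the scanner. Answer: no.
6. **Action before session III.** Section 8.4.1, on specific withdrawal criteria, is marked as not applying, and Section 8.7 names only hypoglycaemia. Section 4.3 uses a recent episode of rhabdomyolysis to bar entry, but no re-check before session III is described. Answer: no stated rule.

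Counts that follow:

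- Endurance sessions with on-site CK specified: 1 of 2 (III, not II).
- Extra readings if CK is added at session II: 1 per patient × 6 planned patients = 6. Section 1 reports four participants so far and one further patient made eligible by the lower age limit, so 4 + 1 = 5 on that account. If CK is already being run at session II, the number is zero.
- Patients still to benefit, if the four had already finished both sessions (not stated): 6 − 4 = 2 on the planned number, or 5 − 4 = 1 on the Section 1 account.

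**The case against.** The strongest reply is that this is a slip of wording. The CK sentence sits in a block headed for sessions II and III together, where the other steps apply to both. Its 3-hour limit matches the 3-hour rest and final sample scheduled in both. With the unrestricted CK and myoglobin entries in the Summary, a reasonable investigator might run CK after each session anyway. This stands as a plausible reading, but it does not settle the matter: the session III wording appears twice, and Sections 8.1.2 and 8.3 do not supply the missing instruction.

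A second reply is that other safeguards exist, and they do. Section 5.3 stops exercise for physical complaints. Section 8.4 lets the investigator withdraw a patient for urgent medical reasons, and Section 8.5 foresees withdrawal for complaints during exercise. Section 9.4 allows further tests when following up an adverse event, and the burden footnote promises monitoring. These make unreviewed re-exercise unlikely. Most of them, however, depend on someone first recognising an event, which is what a CK result would help with.

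A reader might also infer more than the documents support:

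- **That no CK is measured before session III.** Session I includes it, and the Summary list may cover session II.
- **That the protocol forbids postponing session III.** The Summary says "time between study sessions II and III will be 7 days", which is a schedule. No text bars deferral.
- **That the protocol leaves rhabdomyolysis after session II unmanaged.** Investigator discretion and adverse event follow-up apply, although neither names it.
- **That a 7-day gap breaches the two-month window in Section 4.3.** That is an entry criterion, and the two months may attach only to renal failure. It measures no risk at session III.
- **That the spectroscopy comparison is compromised.** This would need an episode to occur and every safeguard to miss it. The documents show no changed endpoint or conclusion.

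**Conclusion.** The concern holds in a limited form. As written, the on-site CK check for rhabdomyolysis is specified only after the last exercise exposure, and nothing assures that a session II result is available and reviewed before session III. The spacing and the lack of a named rhabdomyolysis rule support this point but are not separate faults.

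Severity is minor: a cheap improvement in patient safety. If the session III wording is a slip, that part needs only a correction of wording. The chance of a missed episode cannot be estimated, because the documents give no event rate. The usefulness of a CK reading at three hours is taken from the protocol's own choice of time and has not been tested here.

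**What to change.** In Section 3 and the Summary, state that on-site CK is run on the existing 3-hour post-exercise sample after both session II and session III. Add that the session II result and the 24-hour call are reviewed before session III, and that session III is deferred or withheld if rhabdomyolysis is suspected, using a CK threshold set by the clinicians. Word the II to III interval as a minimum of 7 days, as is already done for I to II, so that deferral fits the schedule.

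The cost is amendment wording and up to six CK readings on a sample already drawn. The downside is an occasional session III that is delayed or missed, which in a crossover of six patients would be felt.
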